In addition, IGF-I, IGFBP-3 and MOD-4023 serum levels will be assessed every 6 months on day 3 or 4 post dosing. Once a year, patients will be required to attend another visit on dosing day (in addition to the semi-annual visit on day 3 or 4 post dosing) where the following additional assessments will be conducted (on top of the three and six months assessments): antigenicity (anti MOD-4023 antibodies), MOD-4023 serum levels, Physical examination, Vital signs, Parameters of glucose metabolism (fasting glucose, fasting insulin and HbA1c), Routine safety laboratory (biochemistry, hematology and urinalysis), other hormonal levels (TSH, free T4, free T3 and cortisol), lipid metabolism parameters, pubertal status, ECG, bone age, fundoscopy (if required), and for males that are 13 years old and above: LH, FSH and testosterone. For females that are 12 years old and above: LH, FSH and estradiol.

All patients switching to 0.66 mg/kg/week (e.g. patients from cohort 1 & 2 treatment arms) will be required to attend a site visit after 3 months (on day 3 or 4 post-dosing) for the process following evaluations: physical examination and vital signs, patient's height and weight, concomitant medications, glucose metabolism parameters (fasting glucose, insulin and HbA1c), antigenicity (anti MOD-4023 antibodies), routine safety laboratory (biochemistry, hematology and urinalysis) and IGF-I and IGFBP-3 serum levels.

In case the switch to the 0.66 mg/kg/week dose is on month 9 visit, the 3 months follow up visit will take place on dosing day. Additional visit will take place 3-4 days post dosing in which only IGF-I, IGFBP-3 and MOD-4023 serum levels will be measured.

Patients from cohort 3 should continue with their routine visit schedule.

Patients will sign a separate informed consent to be eligible to enter OLE and LT-OLE. Patients who have already entered OLE will be re-consented for LT-OLE. Patients from Cohorts 1 and 2 will be instructed by the investigator about the transition to the higher dose of MOD-4023 (0.66 mg/kg/week) and will also be re-consented.

Annual extension notification will be submitted to local EC/IRB.

Effective Date: Date of final electronic approval

Treatment Period V (LT-OLE-PEN) – until marketing approval**First year of LT-OLE-PEN period**

Upon regulatory clearance of protocol amendment 9 and sponsor written approval, patients will be requested to come to the clinic for PEN Visit 1(PEN V1).

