The following assessments will be conducted every 6 months (± 2 weeks) on day 4 (-1) post dose on top of the 3 month assessments:

- IGF-I, IGFBP-3 and MOD-4023 serum levels.
- Once a year, patients will be required to attend another visit **on dosing day** (in addition to the semi-annual visit on day 3 or 4 post dosing) where the following additional assessments will be conducted (on top of the three and six months assessments):Anti-MOD-4023 antibodies;
- MOD- 4023 serum levels
- Physical examination;
- Vital signs;
- Parameters of glucose metabolism (fasting glucose, fasting insulin and HbA1c);
- Other hormonal levels (TSH, free T4, free T3, cortisol);
- Parameters of lipid metabolism;
- Routine safety laboratory (biochemistry, hematology and urinalysis);
- Pubertal status;
- ECG;
- Bone age;
- For males above the age of 13 - LH, FSH and testosterone. For females above the age of 12 - LH, FSH and estradiol;
- Fundoscopy (if indicated).

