4.3 Study Flow Chart OLE (Periods III, IV, V)

Period III (starting 2nd year of treatment, i.e. first year OLE)

OLE	Day 1 and Month 1 OLE ¹	Every 3 months OLE visit	Every 6 months OLE visit	Every 12 months
	Visits 1-2			
Previous and concomitant medication	Х	Х		
Actual HT	Х	Х		
Body weight	X	Х		
Physical examination	Х	Х		
Vital signs	Х	Х		
Injection site reaction (local tolerability)	Х	X		
ECG				X
Pubertal status (Tanner)				X
BA (Greulich-Pyle)				Х
Routine safety biochemistry/ hematology and urinalysis	Х	X		
IGF-I and IGFBP-3	X	X		
Somatrogon serum levels	X	X		
Anti-somatrogon antibodies			X	
Thyroid status (FT4, T3, TSH)	X	Х		
Cortisol levels	X	Х		
Fasting glucose, fasting insulin	X	Х		
HbA1c	Х	Х		
Lipid panel	X	X ²		
Lipoprotein				Х
AE assessment	Х	Х		
Fundoscopy ²				X ²
Somatrogon administration	X			
Training for study medication administration	Х			
Dispense study medication	X	X		
Dispense patient diary	X	X		
Return and accountability of study medication	Х	X		
Return and review of patient diary	X	X		

¹ Only patients who received Genotropin in the main study and switched to somatorogon will attend these 2 visitsapplicable only for first year of extension

² Earlier if there are clinical signs of intracranial hypertension

Periods IV (Treatment with 0.66 mg/kg)

OLE	Every 3 months OLE visit - day 4 (-1) post dose	Every 6 months OLE visit – day 4 (-1) post dose	Every 12 months OLE and EOS when marketing approval received - on dosing day
Auxology measurements: Actual HT measured on a calibrated stadiometer and body weight measurement	Х		
Adjustment of dose for weight	Х		
AEs	Х		
Local tolerability	Х		
Concomitant medication	Х		
Dispensing of drug	Х		
IGF-1, IGFBP-3 and somatrogon serum levels		Х	
Anti-somatrogon antibodies			X
Physical examination			X
Vital signs			X
Parameters of glucose metabolism (fasting glucose, fasting insulin and HbA1c)			Х
Other hormonal levels (TSH, FT4, T3, cortisol)			X
Parameters of lipid metabolism			Х
Routine safety laboratory (biochemistry, hematology and urinalysis)			Х
Pubertal status			Х
ECG			Х
BA			X
Lutinizing hormone (LH), follicle stimulating hormone (FSH) and testosterone. ³			Х
LH, FSH and estradiol ⁴			X

³ For male patients that are on the age 13 years old and above ⁴ For female patients that are at the age of 12 years old and above

Period V LT-OLE PEN – First 12 Months

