9.2 Antibodies

Anti-somatrogon antibody (ADA), anti-somatrogon neutralizing antibody, and anti-hGH neutralizing antibody will be tested at month six and month 12 in Period III and then every six months thereafter. The results of the antibody testing will be summarized for each test at each of the OLE and PEN time points tested. The titer and specificity (anti-hGH and CTP) of confirmed ADA will be summarized. The anti-somatrogon and anti-hGH neutralizing antibody status (positive or negative) are only assessed when a patient is confirmed positive for ADA, so any sample that has not shown somatrogon specificity will be considered negative for NAb. The numeric values for titer will be summarized by median, min and max.

Overall incidence of TEAEs and injection site reactions will also be summarized by ADA status.

HV, HT SDS, and peak IGF-1 SDS will be summarized for each reporting period by ADA status.

ADA status will be assigned on a rolling or dynamic basis. A patient is only considered ADA positive at the beginning of the year in which they test positive and for the remainder of the study.

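### ADA-positive status is back-dated to the start of the year of the first positive sample and never reverts, which tends to dilute contrasts by ADA status

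*SAP*

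**What the plan says.** SAP 9.2 gives the rule: patients are to be "only considered ADA positive at the beginning of the year in which they test positive and for the remainder of the study". Status therefore begins at the start of the reporting year that contains the positive sample, and nothing returns a patient to negative.

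The same section plans the outputs that use this status. "Overall incidence of TEAEs and injection site reactions will also be summarized by ADA status", and HV, HT SDS and peak IGF-1 SDS are split by it in each reporting period. In SAP 11.1 the split appears in Tables 10 and 11, 14.4.2.1 to 14.4.2.9 and 14.4.3.1 to 14.4.3.7.

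On sampling, SAP 9.2 says that antibodies "will be tested at month six and month 12 in Period III and then every six months thereafter". The Period IV schedule differs:

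- The SAP 4.3 flow chart for Period IV marks antibodies only in the column "Every 12 months OLE and EOS when marketing approval received - on dosing day".
- Protocol 5.3 says "Once a year, patients will be required to attend another visit" and lists the antibody test there, "on top of the three and six months assessments):Anti-MOD-4023 antibodies".
- Protocol Appendix 3 has no antibody test at the routine month 3, 6 or 9 visits.
- Protocol 5.3 adds one antibody sample 3 months after a patient switches to 0.66 mg/kg/week.

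SAP 6 reports Periods III and IV in 12-month intervals. SAP 7.1 keeps all analysis descriptive.

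**The concern.** A year's status is decided by a sample drawn during that year or at its end, so later information classifies earlier outcomes. The positive group then contains time before the positive test, some of it before seroconversion. Because status never reverts, it also contains time after a transient positive has cleared.

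Safety is the primary objective of the extension analysis (SAP 3.1.1), and antibody formation is the second listed safety endpoint (SAP 3.2.1). Only 53 patients started the OLE (SAP 4.1), so moving a few patients can visibly change an annual ADA-positive row. If antibodies do affect growth, IGF-1 SDS or adverse events, tables built on this status will tend to show less of that effect than exists.

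**Working it through.** The plan states no figure on this point, so there is none to reproduce. The check applies the SAP 9.2 rule to each sampling schedule.

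**1. Months before the first positive sample that are tabulated as ADA-positive.** Sampling times come from Protocol 5.2, 5.3, 5.4 and Appendices 2 to 5, SAP 4.3 and SAP 9.2. Assumptions not in the documents: seroconversion is uniform over the year, antibodies persist until the next sample and are detected there, and a month-12 sample belongs to the year ending.

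| Schedule (sample months) | Possible values | Mean | Whole year pre-test |
|---|---|---|---|
| Period IV as scheduled (12) | 12 | 12 | 100% |
| Period IV on the SAP 9.2 text (6, 12) | 6 or 12 | (6 + 12)/2 = 9.0 | 50% |
| Period IV, switch at start of year (3, 12) | 3 or 12 | 0.25×3 + 0.75×12 = 9.75 | 75% |
| Period III, and Period V from year 2 (6, 12) | 6 or 12 | 9.0 | 50% |
| Period V year 1 (1, 3, 6, 9, 12) | 1, 3, 6, 9 or 12 | (1×1 + 2×3 + 3×6 + 3×9 + 3×12)/12 = 88/12 = 7.3 | 25% |

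Under six-monthly sampling, a patient who is negative at month 6 and positive at month 12 is counted positive for the whole year, despite an observed negative result within it.

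**2. Attenuation among new converters in the conversion year.** Let *f* be the fraction of the year before conversion. Suppose converters have the ADA-negative event rate until they convert and *RR* times that rate afterwards. Then the apparent ratio is *f*×1 + (1 − *f*)×*RR*.

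| Mean conversion time | *f* | *RR* = 2 | *RR* = 3 |
|---|---|---|---|
| Month 3 | 0.25 | 1.75 | 2.5 |
| Month 6 | 0.50 | 1.5 | 2.0 |
| Month 9 | 0.75 | 1.25 | 1.5 |

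This is rate arithmetic. The SAP tabulates patient incidence, so the figures show direction and rough size only.

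**3. The whole positive group in a given year.** Earlier converters are carried forward and are not affected by back-dating in that year. The documents give no ADA counts, so the share of new converters is assumed. For *RR* = 2 and mid-year conversion:

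- new converters 25% of the group: 0.75×2 + 0.25×1.5 = 1.875;
- new converters 50% of the group: 0.5×2 + 0.5×1.5 = 1.75.

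Transient positives carried forward would dilute later years further. Nothing in the documents lets that be sized.

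**4. The alternative label under annual sampling.** If status is set by the last sample at or before the start of the interval, the conversion year is labelled negative for all 12 months. With uniform conversion, 6 of those months on average are truly positive. The misplaced 6 months move to the other group, and the net effect on the ratio depends on group sizes that the documents do not give.

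**The case against.** The strongest reply is that seroconversion dates are known only to lie between two samples and that HV is a 12-month quantity, so any single label for the conversion year is a convention. That stands. Step 4 shows that replacing the rule outright would mislabel in the other direction, so the documents do not support that stronger remedy.

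Three further points also stand, and they limit the claim:

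- The SAP does not say whether a month-12 sample belongs to the year ending or the year starting. SAP 9.6 uses the first visit of each 12-month period as the laboratory baseline. If the boundary sample counted in the new year, the whole-year back-dating in Period IV would disappear.
- Cohort 1 and 2 patients have an antibody sample 3 months after switching dose, so a first positive there need not cover a full pre-test year. When the switch is at a month 9 visit, Protocol 5.3 places that follow-up on dosing day, so it adds no earlier sample.
- Genotropin switchers have anti-hGH but not anti-MOD-4023 testing in the Main Study (Appendix 1). Appendix 2 gives them a pre-OLE anti-MOD-4023 sample only at Visit 0, which is for patients with a treatment gap. A rule based on prior samples needs an added assumption for the rest.

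It can also be said that the summaries are descriptive and that listings of antibody titers, antibodies with efficacy data, and adverse events allow patient-level checks. That is fair, but a listing does not correct the summary tables, and no planned table separates transient from persistent positives.

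**Conclusion.** The rule back-dates ADA status and never reverts it, and this tends to attenuate contrasts by ADA status. In Period IV, all 12 months precede the test for a first positive at a routine month-12 visit, given the year-ending reading of that sample. Under six-monthly sampling it is 6 or 12 months. For new converters in the conversion year only, a rate ratio of 2 would appear as about 1.5, with a range of 1.25 to 1.75 for conversion at month 9 to month 3. Back-dating attenuates the full positive group less.

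A reader might infer that the tables will show no effect of ADA whatever the truth. The arithmetic does not support that: a ratio of 2 or 3 is reduced but stays above 1. A reader might also infer that every back-dated month was truly negative. True onset is unknown; what is certain is that these months precede the positive test. Nor does the plan attribute outcomes to antibodies in a causal sense. It tabulates them in the ADA-positive group without a hypothesis test.

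The sizes rest on assumed conversion times and group shares. The back-dating, the lack of reversion and the conflict over sampling frequency rest on the text alone.

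**What to change.** 1. Reconcile the six-monthly statement in SAP 9.2 with the annual Period IV schedule in SAP 4.3, Protocol 5.3 and Appendix 3, and state which reporting year a month-12 sample belongs to.
2. Keep the current rule and add a second classification beside it. Tabulate TEAEs and injection-site reactions by the last ADA result on or before onset. Tabulate annual HV, HT SDS and IGF-1 SDS by status at the start of the interval. As a stated assumption, treat Genotropin switchers without a pre-OLE anti-MOD-4023 sample as negative at OLE start.
3. Define transient and persistent positivity, and show the two separately.

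The cost is programming a time-dependent flag on data already planned for Listings 16.2.9.6 (antibody titers) and 16.2.7.1 (adverse events). No new samples or visits are needed. The downside is that the added classification counts patients who converted between samples as negative for up to a year. The two versions should therefore be read together, as early and late bounds on onset. Where they agree, the result does not depend on the unknown conversion date.

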9.3 Injection Site Reactions and Pain

Incidence of injection site reaction (ISR) AEs will be summarized by SOC and PT, including pain, redness, bruising, swelling, or itching at the injection site. Summaries will be provided for each 12 month period, and during Period V on PEN.

The pain scores will be summarized with number of overall patients at the beginning of each year as the denominator. For each patient, ISR pain score will be summarized by maximum severity for each period. Missing values will be considered "hurts worse."

ISR erythema/redness, bruising, induration/swelling, itching, and tenderness scores will be summarized with number of overall patients at the beginning of each year as the denominator.

For each patient and reaction type, symptoms will be summarized by maximum severity. Missing values will be considered "severe."

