5.4 LONG-TERM OPEN LABEL EXTENSION PEN (LT-OLE-PEN) PERIOD V- UNTIL MARKETING APPROVAL

5.4.1 First year of LT-OLE-PEN period

5.4.1.1 PEN Visit 1 (PEN V1) – Dosing Day

Upon regulatory clearance of protocol Amendment 9 and sponsor's written approval, patients will be requested to come to the clinic for a visit named PEN Visit 1 (PEN V1). PEN V1 will occur on a planned dosing day, sites should make any effort to schedule this visit according to the current visit schedule and consider to combine visits in order to minimize the burden on the patients. Patients should arrive at the clinic prior to dosing. The visit will serve as 'baseline' to the LT-OLE-PEN period, in which the consent/assent form for the LT-OLE-PEN period will be signed. Patients should return used and unused vials that were dispensed during the study and kept at patient home. Site staff should remind the patients to bring all vials dispensed during the study (used and unused) before the visit.

OPKO Biologics	Protocol for Clinical Study CP-4-004	Page 61 of 133
Effective Date: Date of final electronic approval		

Prior to rolling over into the LT-OLE-PEN period, specific period inclusion/exclusion criteria should be assessed (as specified in section [4.1](#)). In addition changes in status of ongoing AEs or concomitant medications since completion of the LT-OLE period IV.

During PEN V1, the patients will be trained on the use of the PEN, the PEN will be dispensed, and the first PEN dose will be administered at the clinic by the parents/legal guardians. Patient will continue his/her treatment with the same dose level as before the switch to PEN. Patients will be provided with updated patient diary, instructions for use and dosing instructions.

The following will be done during PEN V1, pre dose:

- Auxology measurements (actual height measured on calibrated stadiometer);
- Body weight measurement;
- Adjustment of dose for weight;
- AEs;
- Urine pregnancy test for females of child bearing potential (In case of positive result please refer to section [7.4](#));
- Local tolerability;
- Concomitant medication;
- Dispensing of drug;
- Return of all used and unused vials;
- IGF-I, IGFBP-3 and MOD-4023 serum levels (PK);
- Anti MOD-4023 antibodies (ADA);
- Physical examination;
- Vital signs;
- Parameters of glucose metabolism (fasting glucose, fasting insulin and HbA1c);
- Routine safety laboratory (biochemistry, hematology and urinalysis);
- Other hormonal levels (TSH, free T4 and cortisol);

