Appendix 2: Schedule of Assessments – 12-Month Open Label Extension (OLE) – Period III

Assessments	OLE visit #	FIRST YEAR OLE STUDY MONTH					
		follow up Visit ¹	Day 1 & Month 1 ²	Month 3	Month 6	Month 9	Month 12
		Visit 0	Visits 1-2	Visit 3	Visit 4	Visit 5	Visit 6
Previous and concomitant medication			X	X	X	X	X
Actual height			X	X	X	X	X
Body weight			X	X	X	X	X
Physical examination			X	X	X	X	X
Vital signs			X	X	X	X	X
Injection Site Reaction (local tolerability)			X	X	X	X	X
ECG							X
Pubertal status (Tanner)							X
Bone age (Greulich-Pyle)							X
Routine safety biochemistry/hematology and urinalysis		X	X	X	X	X	X
IGF-I and IGFBP-3		X	X	X	X	X	X
MOD-4023 serum levels		X	X	X	X	X	X
Anti-MOD-4023 antibodies		X ³			X		X
Thyroid status (free T4, free T3, TSH)			X	X	X	X	X
Cortisol levels			X	X	X	X	X
Fasting glucose, fasting insulin		X	X	X	X	X	X
HbA1C		X	X	X	X	X	X
Lipid panel			X	X	X	X	X
Lipoprotein							X
AE assessment			X	X	X	X	X
Fundoscopy							X ⁴
MOD-4023 administration			X				
Training for study medication administration			X				
Dispense study medication		X	X	X	X	X	X
Dispense patient diary		X	X	X	X	X	X
Return and accountability of study medication			X	X	X	X	X
Return and review of patient diary			X	X	X	X	X

¹ Applicable only to patients who were off-treatment for over XXXXXXXXXX between Main Study Month 12 and Visit 1 OLE.

² Applicable only to patients who received Genotropin in the Main Study and switched to MOD-4023 will attend the following visits:

Day 1 is Month 12 visit of the Main Study in which the patient will be trained on medication administration and Visit 2/OLE will be 28 days + 4 (-1) days after the first MOD-4023 injection.

³ Applicable for Genotropin patients

⁴ Earlier if there are clinical signs of intracranial hypertension.

OPKO Biologics	Protocol for Clinical Study CP-4-004	Page 114 of 133
Effective Date: Date of final electronic approval		

Appendix 3: Schedule of Assessments – Long-Term OLE (LT-OLE) Period IV from Second Year of OLE/Third Year of Treatment until switch to LT-OLE-PEN period

Assessments	follow up Visit ¹	First Month 3 visit ² (on day 3 or 4 post-dosing)	Early termination visit ³	LT OLE visits by Month over each year until switch to LT-OLE-PEN period				
				Month 3 visit	Month 6 visit	Month 9 visit	Month 12 each year and End of Study Visit	
Visit 0	Visit 1a	On Dosing Day	day 4 (-1) post dose	day 4 (-1) post dose	day 4 (-1) post dose	day 4 (-1) post dose	On Dosing Day	day 4 (-1) post dose

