Appendix 4: Schedule of Assessments – Long-Term OLE PEN (LT-OLE-PEN) Period V first year

Assessments	PEN Visit 1 (PEN V1)	PEN Visit 2 (PEN V2) 4 weeks (+1) after PEN visit V1	LT OLE PEN visits by Month over the first year			
			Month 3 visit (±2 week)	Month 6 visit (±2 week)	Month 9 visit (±2 week)	Month 12 (±2 week) ¹
Informed consent/ assent	X					
Auxology measurements (actual height measured on calibrated stadiometer)	X		X	X	X	X
Body Weight measurement	X	X	X	X	X	X
Adjustment of dose for weight	X	X	X	X	X	X
AEs	X	X	X	X	X	X
Local tolerability	X	X	X	X	X	X
Concomitant medication	X		X	X	X	X
Dispensing of drug	X	X	X	X	X	X
Return of used drugs	X ²	X	X	X	X	X
Training on PEN	X	X ³				
Fundoscopy- If required	X	X	X	X	X	X
IGF-I, IGFBP-3	X	X	X	X	X	X
MOD-4023 serum levels	X	X	X	X	X	X
Anti-MOD-4023 antibodies	X	X	X	X	X	X
Physical examination	X	X	X	X	X	X
Vital signs	X	X	X	X	X	X
Glucose metabolism (fasting glucose & insulin, HbA1c)	X		X	X		X
Other hormonal levels (TSH, free T4, cortisol)	X		X	X		X
Parameters of lipid metabolism	X		X	X		X
Routine safety laboratory (biochemistry, hematology and urinalysis)	X		X	X		X
Urine pregnancy test ⁴	X	X	X	X	X	X

¹ In case ET/EOS visit is conducted all assessment should be done at one visit with no split.

² Return of used and unused MOD-4023 vials.

³ If required.

⁴ For females of child bearing potential. In case urine pregnancy test is positive, please refer to section [7.4](#) in the protocol.

OPKO Biologics	Protocol for Clinical Study CP-4-004	Page 117 of 133
Effective Date: Date of final electronic approval		

	PEN Visit 1 (PEN V1)	PEN Visit 2 (PEN V2) 4 weeks (+1) after PEN visit V1	LT OLE PEN visits by Month over the first year			
			Month 3 visit (±2 week)	Month 6 visit (±2 week)	Month 9 visit (±2 week)	Month 12 (±2 week) ¹
Pubertal status ¹	X		X	X	X	X
ECG around Tmax (7-12 hours post dose) ²						X
Bone age	X ³					X
LH, FSH and Testosterone ⁴	X					X
LH, FSH and Estradiol ⁵	X					X
Provide patient diary and return of completed diaries		X	X	X	X	X

¹ In case the patient becomes pubertal, childbearing potential and refraining from sexual activity will be discussed with the patient.

² In case not possible to conduct the ECG around Tmax at the 12 months visit, it can be performed on month 12± 3 weeks (7-12 hours post dose).

³ Bone age measurement will be performed in case the previous assessment was done more than 6 months prior to this visit.

⁴ For male patients that are at the age of 13 years and above.

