7.4 Data Handling and Missing Data

Because of the observational nature of this study, missing data in general will not be imputed, except for:

1. specific items associated with AEs as specified in Section 9.1;

2. missing day or month will be imputed to the 1st of each if needed for calculations, unless this imputation contradicts a previous date (such as between start and stop dates). In this case, the imputed date will be last day or month, or be missing and presented as "ongoing."

Unscheduled assessments or multiple results within a specified visit window will be listed, but not used in the visit summary. The assessment closest to the scheduled visit date will be used.

Early termination assessments will be assigned to the appropriate annual interval based on treatment month within a period.

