A listing of TEAEs that lead to withdrawal from the study will also be provided.

Missing values will be treated as missing except for causality, intensity, and outcome of an AE, at which occurrence a "worst case" approach will be taken in the analysis. Thus, if causality is missing the AE will be regarded as related to the investigational medicinal product (IMP), if the intensity is missing the intensity of the AE will be regarded as severe, and if the outcome is missing and the stop date is not provided the outcome is regarded as "ongoing." If the classification of SAE (seriousness) is missing, all efforts should be made prior to database lock to make sure that this information is available.

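### SAP 9.3 counts missing injection site scores as the top grade without limiting this to recorded reactions, so Tables 14.3.4.3 and 14.3.4.4 can report blanks as severe

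*SAP*

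**What the plan says.** SAP 9.3 sets the same pattern for two groups of scores.

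- Pain: "ISR pain score will be summarized by maximum severity for each period. Missing values will be considered" 'hurts worse'.
- Redness, bruising, swelling, itching and tenderness: for each patient and reaction type, "symptoms will be summarized by maximum severity. Missing values will be considered" 'severe'.

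Both summaries use the "number of overall patients at the beginning of each year as the denominator". On the scales in Protocol Appendix 8, the imputed values are the top grades: face 5 of 0 to 5 for pain, and grade 3 of 0 to 3 for redness, bruising, swelling and itching. Tenderness has no scale there. The results go to Table 14.3.4.3 (overall) and Table 14.3.4.4 (annual), with by-visit scores in Listing 16.2.9.7.

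Three other places bear on the rule.

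- SAP 9.1 also uses a worst-case approach, but for an attribute of an event already on file: "if the intensity is missing the intensity of the AE will be regarded as severe".
- SAP 7.4 states that "missing data in general will not be imputed, except for" the AE items of Section 9.1 and incomplete dates.
- Protocol 5.7.3 has the investigator inspect the injection site at a visit when there is a reaction to see. Otherwise it relies on history and the patient diary.

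**The concern.** A per-patient maximum combined with top-grade imputation is very sensitive to blanks. Once a blank is set to the top grade, no observed score can bring the maximum down, however many clean scores the patient has. SAP 9.3 does not define a missing value, does not require that a reaction was recorded, and does not say whether imputation comes before or after the maximum is taken. Because the denominator is everyone who started the year, a patient with no score at all, such as an early leaver, also has to be placed somewhere. The only placement the text offers is the top grade.

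The way scores are collected adds to the problem. If the site is graded mainly when a reaction is seen, a blank may mean that there was none, and the rule would report it as the worst possible reaction.

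Local injection site assessment is a listed safety endpoint (SAP 3.2.1), and safety is the primary objective of the extension analysis (SAP 3.1.1). A reader of the two score tables could not tell a severe reaction from an absent record. The tables could also disagree with the injection site AE tables. Under Protocol 5.7.3 a moderate or severe reaction seen at a visit is an AE, whereas an imputed severe score has no AE behind it.

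**Working it through.** The plan states no figure for this rule, so there is none to reproduce. The check sets the rules side by side and then illustrates the size.

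**1. The rules compared.**

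| | SAP 9.1 (AE intensity) | SAP 9.3 (scores) | SAP 9.4 (IGF-1 SDS above 2) |
|---|---|---|---|
| What must exist first | A recorded AE | Nothing stated | A result |
| Missing value | Severe | Top grade | Not imputed |

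SAP 9.4 is also a once-per-patient summary over an interval, and it does without imputation.

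**2. One patient.** Pain scores 0, 0, blank, 0. Maximum with the blank set to 5: 5. Maximum over observed scores: 0.

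**3. Illustration, literal reading.** Inputs: 53 patients started the OLE (SAP 4.1); k = 4 scores a year (visits at months 3, 6, 9 and 12); m = the share of scores that are blank, which is **assumed** because the documents give none. Two patterns of blanks:

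- fully clustered (the same patients miss everything): share forced to the top grade = m
- independent between scores: share = 1 − (1 − m)^k

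At m = 2%: clustered 2.0%, or 53 × 0.02 = 1.1 patients; independent 1 − 0.98^4 = 7.8%, or 53 × 0.0776 = 4.1 patients.

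| m (assumed) | Clustered | Independent, k = 4 |
|---|---|---|
| 1% | 1.0% (0.5 of 53) | 3.9% (2.1 of 53) |
| 2% | 2.0% (1.1 of 53) | 7.8% (4.1 of 53) |
| 5% | 5.0% (2.7 of 53) | 18.5% (9.8 of 53) |

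**4. Patients with no score.** Each one placed at the top grade adds 1/53 = 1.9 percentage points in OLE year 1.

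**5. The counting unit.** Appendix 8 has the pain face circled in the patient diary and dosing is weekly, but Listing 16.2.9.7 is by visit. The documents do not say which scores enter the maximum. If all 52 weekly diary scores did, independent blanks at m = 2% give 1 − 0.98^52 = 65.0%, or 34.5 of 53. The clustered figure stays at 2.0%.

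**6. Narrow reading.** Suppose the rule applies only to a recorded reaction with no grade. With an assumed reaction rate r per visit and an assumed share q of grades missing, the share is 1 − (1 − rq)^4. For r = 10% and q = 5%: 1 − 0.995^4 = 2.0%, about 1 of 53, against 18.5% on the literal reading at 5% blank. Over r = 5% to 20% and q = 5% to 10% the range is 1.0% to 7.8% (0.5 to 4.1 of 53). All of these patients did have a reaction.

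**The case against.** The strongest reply is that 9.3 was meant like 9.1: a reported symptom whose grade was left blank. Data capture supports this. The tolerability page records reaction type, frequency and intensity, so a visit without a reaction may generate no score. The literal rule would then put nearly every patient at the top grade, which nobody is likely to have intended. A denominator of all starters also fits patients without a record being counted as reaction-free. This is plausible, but 9.3 does not say it, and a programmer following the sentence would not produce it.

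Worst-case handling of safety data is also a legitimate, prespecified choice that works against the product. That stands as a reason to keep such an analysis available. It does not justify mixing imputed and observed top grades without showing which is which.

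Two stronger readings are tempting, and the documents do not support either.

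- **That 9.3 contradicts 7.4.** Section 7.4 speaks only of what is done in general, and its list is not exhaustive. Section 7.5 substitutes values for censored laboratory results and 9.2 sets untested neutralizing antibody status to negative, and neither is listed in 7.4. A cross-reference is missing; there is no firm conflict.
- **That PEN year 1 will look worse than later years because it has more visits.** Appendix 4 does list local tolerability on six occasions, against four in later PEN years. But the PEN V1 assessments come before the first PEN dose ("The following will be done during PEN V1, pre dose") and SAP Section 6 makes that visit the Period V baseline. The SAP's own first-year PEN chart shows local tolerability only every three months. With five scores and independent blanks at 2%, the share is 1 − 0.98^5 = 9.6%, only 1.8 points above four scores, and with clustered blanks the difference is zero. A maximum over observed scores also rises with the number of visits, and if diary scores are used, visits are not the unit at all.

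**Conclusion.** The point holds as a defect in the wording of SAP 9.3, of minor to moderate weight. Followed as written, the rule lets a single blank override all observed scores and places patients without scores at the top grade. Tables 14.3.4.3 and 14.3.4.4 can then be biased upward and cannot separate severe reactions from absent records.

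The size cannot be fixed from the documents. The illustrative 2.0% to 7.8% of patients (1.1 to 4.1 of 53) rests on the literal reading, four visit scores a year, an assumed 2% missing rate, and blanks between fully clustered and independent. It could be much larger if weekly diary scores enter the maximum. If only recorded reactions were meant, it is small.

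A reader might infer that the plan's injection site safety results as a whole are unreliable. That does not follow. The injection site AE tables (14.3.4.1 and 14.3.4.2) do not use these scores, Listing 16.2.9.7 still shows scores by visit, and the extension analysis is descriptive with no hypothesis tests.

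**What to change.** In SAP 9.3, replace the two missing-value sentences with:

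> Maximum severity is taken over observed scores. A recorded reaction with no intensity is counted as the worst grade, consistent with Section 9.1. Patients with no score in the interval are shown in a Missing row.

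Also state in 9.3 whether diary scores, visit scores or both enter the maximum, and cross-reference the recorded-reaction rule in 7.4. If the conservative view is wanted, keep full worst-case imputation as a labelled sensitivity table that gives the number of imputed scores.

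Cost: a few SAP sentences, one line in 7.4, one extra row in each of the two tables and, optionally, one sensitivity table. No new data are needed. The downside is that the main table becomes less conservative and may understate severity if blanks hide reactions, which the sensitivity table would show. The change does not remove the dependence of a maximum on how many scores a patient has.
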